5.1. Study Design

5.1.1. Describe in detail the experimental design, i.e. from recruitment procedures to study closure.

Design. Forty patients will be enrolled in the proposed work. Participants will be randomly assigned to one of two groups for the 12-week intervention period: (1) usual care; or (2) TEC strategies with enrollment in a weekly regret lottery.

Sample and Setting. The sample will be comprised of patients receiving care at the Corporal Michael Cresenz VA Medical Center (CMCVAMC) in Philadelphia as well as at the Pain-focused Patient Aligned Care Team (P-PACT). This primary care clinic was instituted to provide comprehensive, evidence-based care to patients with chronic non-malignant pain and on opioid therapy. Patients referred to the program are those identified as high-risk related to being on high dose opioid therapy; on combined opioid/benzodiazepine therapy; and/or having a history of substance abuse. A key component of the P-PACT program is improving mobility amongst patients using modalities available through the VA, including physical therapy, yoga and tai chi, which have an evidence base to improve pain, sleep, cognitive and physical function as well as decrease medication use.

Inclusion Criteria	Exclusion Criteria

• Chronic non-malignant pain• High dose opioid therapy• Possession of activated cell phone with text messaging capabilities• Willingness to comply with study requirements	
• Pain of malignant origin• Sensory impairments precluding use of text messaging and activity tracker• Physical disability precluding improvements in physical activity

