Procedures. Eligible patients will be offered participation in this pilot study. The enrollment goal of 40 patients was chosen based on feasibility given the time-frame. Following informed consent, participants will be randomly assigned to one of the two study arms. All participants will be provided individual activity regimens, and be offered physical therapy, yoga, or tai-chi classes at the CMCVAMC. The activity goal will be participation in their activity regimen or classes at least twice per week, a frequency used in other studies promoting activity for chronic pain. Participants will self-report their activity, pain severity, functionality, and opioid use monthly via questionnaire and pill counts. Additionally, all participants will be provided an activity tracker to measure steps taken and instructed on use and data upload procedures. Upon the completion of their 12-week participation, participants are asked to complete an in-person exit survey answering questions about their experience in the study, the use of the FitBit activity watches, as well as the use of the FitBit application.

Those receiving the TEC-linked intervention will be familiarized with the text messaging process and the measures that will be administered via this technology. TEC will consist of a daily personalized text message from a dedicated research assistant reminding the patient to engage in their prescribed physical activity for the day. A second text message at the end of the day will direct the patient to return activity participation, pain severity, functionality, and opioid use data, and upload activity tracker data to the Way to Health (WTH) platform. The behavioral incentive provides the opportunity for subjects who meet their weekly activity goals to enter a lottery to receive either a small (\$30) or large (\$100) financial incentive. The lottery is structured such that subjects have an 18% chance/week of winning the small prize, and a 1% chance of winning the large prize. For those not meeting goals, they will be informed what they would have won had they met their goal. This design has been used in similar studies, with evidence showing the desire to avoid regret can be motivating.

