5.3.3. State how compensation will be provided: ***Voucher***

5.4. **Informed Consent Procedures**

5.4.1. Indicate if informed consent will be obtained and/or if you are requesting a waiver of informed consent or waiver of documentation of informed consent. ***Consent to be obtained***

5.4.2. If the research involves multiple phases, specify for which phases of the research the waiver(s) is/are being requested.

N/A

5.4.3. Describe circumstances, if any, that may need to be addressed in seeking informed consent (e.g., subjects with impaired decision making ability and the use of a legally authorized representative, etc.)

Not applicable.

5.4.4. If applicable, indicate how study personnel will be trained regarding human subjects protections requirements and how to obtain and document informed consent.

All study personnel will have completed the required human subjects, HIPAA, and information security and privacy trainings at the VA.

5.4.5. **Inclusion/Exclusion Criteria:** Describe the criteria that determine who will be included in or excluded from the study.

5.4.5.1. **Inclusion Criteria**

1) adults age 18 years or older; 2) Chronic non-malignant pain; 3) High opioid therapy; 4) Possession of activated cell phone with text messaging capabilities; and 5) willingness to comply with study requirements.

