5.4.5.2. Exclusion Criteria

1) Pain of malignant origin; 2) Sensory impairments precluding use of text messaging and activity tracker; or 3) Physical disability precluding improvements in physical activity.

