5.10. Information Security

5.10.1. **List the data/information that will be stored (including signed, original informed consent and HIPAA authorization forms, if applicable, case report forms, etc.)**

Stored data and information will include: patient information including name, last 4 of SSN, date of birth, BMI, medical, problem list, signed, original informed consent forms, medication usage, baseline questionnaires capturing participants' sociodemographic information, technology

assessment, and current level of physical activity, any responses from follow-up phone/in-person interviews/surveys.

5.10.2. **Describe the steps that will be taken to secure the data (e.g., training, authorization of access, password protection, encryption, physical controls, Certificates of Confidentiality and separation of identifiers and data).**

All study personnel will complete the required human subjects, HIPAA, and information security and privacy trainings at the VA. Each Veteran who enrolls in this study will be assigned a unique, random patient ID number generated for the purposes of this study. To protect each participant's identity, the link between the Veteran's name, last 4 of SSN, date of birth, and patient ID number will be a password protected file stored on a secure VA server and accessible only to research staff. In all subsequently created analytical files, participants will only be identified by their patient ID number, without inclusion of his/her name, SSN, or date of birth. Subject questionnaires will be either directly inputted into a computer database or written onto paper forms and then transferred to a database at a later time. Interview transcripts will be produced electronically and will be housed on a secure VA server as well. No results will be reported in a personally identifiable manner.

5.10.3. **Indicate how and where data/information will be stored, and specify pertinent security systems.**

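### Entry and randomisation ignore current activity although the lottery rewards a fixed twice-weekly goal, so the effect on activity may be diluted and the arms unbalanced by chance

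*Combined protocol and SAP*

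**What the plan says.** **Goal and incentive (5.1.1, Procedures).** The goal is an absolute frequency, the same for everyone: "The activity goal will be participation in their activity regimen or classes at least twice per week". Lottery entry depends on meeting it: "The behavioral incentive provides the opportunity for subjects who meet their weekly activity goals to enter a lottery". The odds are "18% chance/week of winning the small prize, and a 1% chance of winning the large prize", with prizes of $30 and $100. Nothing ties entry to a change from the patient's own starting level.

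**Activity offered to both arms (5.1.1).** "All participants will be provided individual activity regimens, and be offered physical therapy, yoga, or tai-chi classes at the CMCVAMC". No rule requires a regimen to exceed what the patient already does.

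**Eligibility (5.1.1, 5.1.3, 5.4.5).** The inclusion list covers age, chronic non-malignant pain, high opioid therapy and then "Possession of activated cell phone with text messaging capabilities; and 5) willingness to comply with study requirements". The only exclusion that bears on activity is "Physical disability precluding improvements in physical activity".

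**Source of patients (5.1.1, Sample and Setting).** Recruitment is from the medical centre and from its pain-focused clinic (P-PACT), of which the protocol says: "A key component of the P-PACT program is improving mobility amongst patients using modalities available through the VA". Physical therapy, yoga and tai chi are the modalities named.

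**Baseline data and analysis (5.2.3, 5.10.1, 9.2).** Eligibility and baseline surveys share one visit, and the baseline questionnaires capture "current level of physical activity". Section 9.2 compares changes over time between arms and plans regressions on baseline characteristics as modifiers of efficacy. It does not name baseline activity, and no stratification is described.

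**The concern.** The aim in Sections 3 and 4 is to increase participation and mobility. The exclusion for disability shows that the authors want participants who have room to improve, but it removes only those who cannot improve for physical reasons. It does not address those who already do what the goal asks.

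A patient who attends two classes a week before enrolment, and continues, meets the goal unchanged. The lottery offers this patient nothing extra for doing more, and the message about a forgone prize is not triggered while the goal is met. If such patients are a material share of the 40, the average between-arm difference understates what the incentive does for patients with room to respond. A useful strategy could then look weak in the pilot meant to judge it. With 20 per arm and no stratification, their number may also differ between arms by chance.

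**Working it through.** **Inputs from the protocol.** 40 patients, 20 per arm (5.2.1); 12 weeks and the lottery odds and prizes (5.1.1); no power calculation, since 40 was chosen on feasibility (9.1). There is therefore no power figure to reproduce.

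**Assumptions, none of them in the protocol.** Share p already at goal: 10%, 25%, 40%. Two-sided alpha 0.05, no dropout, constant SD, normal approximation. Illustrative effect d = 0.8 SD in patients with room to respond.

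**Reference point.** Effect detectable with 80% power at 20 per arm: (1.960 + 0.842) x sqrt(2/20) = 0.886 SD.

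**Dilution, worst case.** If patients at goal gain nothing, the average effect is (1 - p) x d. At constant SD the standard error does not change; the effect shrinks. Keeping the same power therefore needs 1/(1 - p)^2 times as many patients.

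| p | Effect retained | Patients for equal power | Power at 20 per arm, d = 0.8 |
|---|---|---|---|
| 0 | 100% | 1.00x | 72% |
| 10% | 90% | 1/0.90^2 = 1.23x | 62% |
| 25% | 75% | 1/0.75^2 = 1.78x | 47% |
| 40% | 60% | 1/0.60^2 = 2.78x | 33% |

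**Partial response.** If patients at goal gain half the effect, the retained share is 1 - p/2, that is 95%, 87.5% and 80%. The multipliers fall to 1/0.95^2 = 1.11, 1/0.875^2 = 1.31 and 1/0.80^2 = 1.56.

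**Chance imbalance.** Suppose 10 of 40 are at goal and 20 go to each arm without stratification. The count in one arm has variance 20 x 0.25 x 0.75 x (20/39) = 1.92, SD 1.39. The between-arm difference in counts has SD 2 x 1.39 = 2.8 patients, or 2.8/20 = 14 percentage points.

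**Lottery.** Expected payout per qualifying week is 0.18 x $30 + 0.01 x $100 = $6.40. Over 12 weeks it is $76.80, if the goal is met every week.

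**Below-goal analysis.** At p = 25% and d = 0.8 in the worst case, 15 below-goal patients per arm give about 59% power, against 47% for all 20 per arm with the diluted effect. A supportive analysis in that group is therefore informative despite its smaller number.

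**The case against.** The case for leaving the plan alone has several good parts.

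- **No rate is given.** A clinic that promotes classes is not a clinic whose patients attend twice a week, and recruitment extends beyond that clinic. A reader might infer that patients already at goal are to be expected in number. The documents support only that they are plausible.
- **Goal attainment is not a planned outcome.** Section 4.1 names the Stanford questionnaire and the tracker, and Section 9.2 compares change. A reader might infer that an imbalance feeds straight into a goal-attainment result, or that patients at goal have nowhere to go. Neither follows: no such result is planned, and these patients can still rise on both measures.
- **The lottery is not the whole intervention.** Daily reminders may move active patients, and the incentive may sustain attendance that lapses under usual care. Regimens are individual, and Section 5.6.1.1 describes a gradual increase in the first month, so some patients may be set more than they now do. Zero gain is the worst case.
- **It is a pilot without a power target.** Enrolling patients as they present is defensible, and the planned regressions could include baseline activity.

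All of this limits the size of the problem; it does not remove it. No rule requires a regimen above current activity, and classes alone satisfy the goal. Comparing change corrects for starting level but does not restore lost room to respond. Change may itself depend on starting level in both arms, since both receive regimens and trackers. Baseline activity is collected but is not assigned to the randomisation or named in the analysis.

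**Conclusion.** The point holds as a design weakness that is cheap to correct. Patients already at the twice-weekly level can be randomised and can qualify for the lottery without increasing activity, and the plan neither balances them between arms nor accounts for them by name.

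The size is unknown. Under the worst-case assumption the retained effect is 90%, 75% or 60% at p = 10%, 25% or 40%, with 1.23, 1.78 or 2.78 times as many patients needed for equal power; partial response reduces these figures. The power figures also rest on an assumed effect, alpha and constant SD.

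A reader might go further and infer a biased comparison or a failed power claim. The documents support neither. Randomisation distributes these patients evenly on average, and Section 9.1 makes no power claim. What is at risk is a weaker, harder-to-interpret effect estimate.

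**What to change.** **Section 5.1.1.** State that baseline activity, as weekly frequency of regimen-type exercise or of physical therapy, yoga or tai chi, is recorded at the eligibility and baseline visit before randomisation. The protocol does not now state that order. Stratify randomisation by at goal or below goal.

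**Section 9.2.** Adjust the between-arm comparison of activity and steps for baseline activity. Name baseline activity as a modifier in the planned regression. Pre-specify the below-goal group as a supportive analysis, with all randomised patients as the main population.

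This handles imbalance and makes any dilution visible; it does not remove dilution from the main estimate.

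**Cost.** One stratification factor, and a check that the baseline question records weekly frequency, since Section 5.10.1 refers only to a level of activity. No patients are lost.

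**Optional.** Restricting entry to below-goal patients would remove the dilution at source, but it narrows the pool in a recruitment window of four months (months 4 to 7). If 10%, 25% or 40% of those now eligible are at goal, 36, 30 or 24 of every 40 would remain. That is a trade-off for the team, not a necessary change.

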5.1.6. Will this study bank/store specimens for future research? **NO**

5.1.6.1. If yes, include information on specimens to be banked/stored.

5.1.6.2. If specimens will be banked/stored, specify location.

5.1.6.3. If the location of the specimen bank is a non-VA site, has the mandatory approval from VA Central Office been obtained through submission of a tissue banking application? **Choose an item.**

5.1.6.3.1. If yes, provide a copy of the response from VA Central Office.

5.1.6.3.2. **IF BANKING SPECIMENS, IT MUST BE AT A VA APPROVED FACILITY. (For additional information, go to the following website http://www.research.va.gov/programs/tissue_banking/, or contact the IRB office.)**

5.1.6.4. If applicable, explain how destruction of banked samples will be substantiated.

5.1.6.5. Do you anticipate using the banked specimens for other studies beyond the defined study period and defined study parameters? **Choose an item.**

5.1.6.5.1. If yes, will you need to re-contact subjects? How will this be done?

5.1.7. Will this study create a data repository for future studies? **NO**

5.1.7.1. If yes, describe and/or provide the following:

5.1.7.1.1. The type of data (identified or de-identified) including what protected health elements are to be collected.

5.1.7.1.2. The source from which data will be collected (e.g., subjects, non-research data repositories, research data repositories, publicly available, VA source, non-VA source).

5.1.7.1.3. How and where the data will be stored (e.g., electronic, paper records, approved VA-owned or VA-leased space).

5.1.7.1.4. How the data will be transmitted, if applicable.

5.1.7.1.5. How the data will be secured during storage, use, and transmission both during the conduct of the research protocol and after the protocol is completed.

5.1.7.1.6. **Plans to store data for future research.** If the data is stored for future research, there must be a description of a research data repository, its location, and its security measures.
[]

5.1.7.1.7. **Plans to share with others including other researchers (VA and non-VA).** If the data were collected through a research project, discussion of whether or not the original informed consent allowed for such reuse of the data and if the reuse is consistent with the HIPAA authorization that was obtained.
[]

5.1.7.1.8. **Justification for the use of any identifiers.**
[]

5.1.7.1.9. **Justification that the data requested represent the minimum necessary to conduct the research.**
[]

5.1.7.1.10. **A discussion of plans for obtaining informed consent and HIPAA Authorization, or for requesting the IRB to waive these requirements.** If the investigator requests that the requirement for a HIPAA Authorization be waived, justification for this request must be included in information submitted to the IRB.
[]

5.1.7.1.11. **In addition to the above, provide a Standard Operating Procedures Manual for the data repository. Contact IRB office for additional details.**

5.2. **Subject Recruitment Methods**

5.2.1. **State how many subjects will be needed:** 40 total subjects, with 20 in each arm of the study.

5.2.2. **Who will be responsible for recruiting potential subjects? Provide titles of individuals.**

The study team will include:

[name] – Principal Investigator
[name]- Co-Principal Investigator
[name]- Project Manager

5.2.3. **How will initial contact with potential subjects be made? (e.g., local clinics, physician referrals, letters to prospective subjects)**

Veterans will be informed of the opportunity to participate in the study by [name] and provided with a copy of a study flyer, and study contact information. The study team will call the veteran 7 days provision of materials. If an individual is interested in the study, they will be asked to review the informed consent and be given the opportunity to ask questions. Once a signed informed consent is returned to the study team, a visit with the veteran will be scheduled to conducted eligibility and baseline surveys. The study team will provide the veteran a wearable device to track step counts and provide instructions to create an account by which they will transmit de-identified step data to the research team and how to access and use the WTH application.

5.2.4. **Will you be using any of the following methods to recruit subjects? (Check all that apply.)**

- Local database for which subjects have NOT given prior permission to be contacted for Research.
- Personal contact with patients over whom you have direct/indirect oversight
- Provider (Clinician) Referrals of potential subjects

5.2.5. Indicate the types of recruitment/advertisement materials that will be used: Check all that apply. Submit copies of recruitment materials, for IRB review.

X Not applicable; none to be used

- Fliers Newspapers Letters Websites Television
- Radio Audio Video Surveys
- Other (Specify, e.g. employee newsletters)

5.2.6. Non-Veteran Subjects will be given a copy of the Notice of Privacy Practices. ***NOT APPLICABLE***

5.3. **Compensation for Participation** - ***YES*** If yes, complete the following.

5.3.1. Summarize any financial compensation that will be offered to subjects.

All participants will receive \$75 to for completing the entire 12-week study. As noted above, they also have the possibility of receiving a financial incentive via a lottery process for meeting activity goals.

5.3.2. Provide the schedule for compensation.

5.3.2.1. Per study visit or session.

N/A

5.3.2.2. Total amount for entire participation.

\$75 if subject completes the entire 12-week study.

5.3.3. State how compensation will be provided: ***Voucher***

5.4. **Informed Consent Procedures**

5.4.1. Indicate if informed consent will be obtained and/or if you are requesting a waiver of informed consent or waiver of documentation of informed consent. ***Consent to be obtained***

5.4.2. If the research involves multiple phases, specify for which phases of the research the waiver(s) is/are being requested.

N/A

5.4.3. Describe circumstances, if any, that may need to be addressed in seeking informed consent (e.g., subjects with impaired decision making ability and the use of a legally authorized representative, etc.)

Not applicable.

5.4.4. If applicable, indicate how study personnel will be trained regarding human subjects protections requirements and how to obtain and document informed consent.

All study personnel will have completed the required human subjects, HIPAA, and information security and privacy trainings at the VA.

5.4.5. **Inclusion/Exclusion Criteria:** Describe the criteria that determine who will be included in or excluded from the study.

5.4.5.1. **Inclusion Criteria**

1) adults age 18 years or older; 2) Chronic non-malignant pain; 3) High opioid therapy; 4) Possession of activated cell phone with text messaging capabilities; and 5) willingness to comply with study requirements.

5.4.5.2. Exclusion Criteria

1) Pain of malignant origin; 2) Sensory impairments precluding use of text messaging and activity tracker; or 3) Physical disability precluding improvements in physical activity.

5.5. Withdrawal of Subjects

5.5.1. Describe how a subject can withdraw from the study.

Subjects may withdraw at any point by informing the study team in person, by written mail or by phone.

5.5.2. Describe any anticipated circumstances under which subjects will be withdrawn from the research without their consent.

None.

5.5.3. Describe the consequences of a subject's decision to withdraw from the research and the procedures for orderly termination of participation by the subject (e.g., the subject contacting the investigator for an end-of-study visit).

Patients choosing to withdraw early in the study will not receive the total compensation as described above, but will receive pro-rated payment of \$6/wk for each week completed. Patients are free to, at any time, contact the study team to be removed from the study. Withdrawn patients will be asked to complete an exit survey with the option of completing in-person or over the phone answering questions about their experience in the study, the use of the FitBit activity watches, as well as the use of the FitBit application.

